6.65 Dose Modification during IL-2 Therapy

- a) Treatment with IL-2 is continued until completed or until Grade 3 or 4 toxicity (or Grade 2 neurologic or cardiac toxicity; Grade 4 neutrophils or bilirubin; or platelets $< 10,000/\text{mm}^3$ with transfusions) occurs at which time IL-2 is discontinued until a return to Grade 1 toxicity, at which time IL-2 therapy will be resumed at 50% of the initial dose. If Grade 3 or 4 toxicity, or Grade 2 neurotoxicity or cardiac toxicity, recurs after resumption of the reduced dose of IL-2 then IL-2 is discontinued and not restarted.

- b) Reduction or discontinuation of IL-2 therapy due to toxicity does not alter the IL-2 treatment schema (Section 6.61.b.ii). If temporarily interrupted, IL-2 therapy is resumed according to the day of the original schedule. Any doses missed due to toxicity are not administered, and total duration of therapy is not extended beyond the original plan at initiation of IL-2 therapy.

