6.66 Toxicities of IL-2 Therapy

- a) High-dose IL-2 administered by CIV results in dose and time dependent toxicities which peak toward the end of the induction course. The most common clinical toxicities seen during induction

IL-2 are of a flu-like syndrome with fever, chills, weight gain, nausea, diarrhea, and rash.

- b) Capillary Leak Syndrome (CLS): The CLS is characterized by peripheral or pulmonary interstitial edema and/or ascites, and "sepsis-like" physiology, i.e., decreased systemic vascular resistance and increased cardiac output. Dose modifications are made for specific organ system toxicity, as per Section 6.65.
- c) Hypotension: Mild hypotension with systolic blood pressure (SBP) 10-20% below baseline is common in patients receiving induction IL-2.
 - i) Asymptomatic patients with SBP > 90 mm Hg should be monitored closely.
 - ii) Any symptomatic patient (regardless of the SBP) and all patients with SBP ≤ 85 mm Hg should be treated immediately with a fluid bolus of NS, 5-7 ml/kg (STAT x 1-2) which may be supplemented with red cell transfusions or colloid infusion. Hypotension which does not respond to fluid therapy should be treated with low-dose dopamine or a phenylephrine infusion, and IL-2 therapy should be interrupted until hypotension resolves.
 - iii) Grade 3 hypotension which does not respond to crystalloid/colloid therapy requires:

IV pressors, preferably phenylephrine (rather than dopamine).

Discontinuing IL-2 infusion

d) Arrhythmias:

- i) Sinus Tachycardia: is common, especially during fever, and is not an indication for intervention.
- ii) Supraventricular Tachycardia: Occurs in $< 10\%$ of adult patients and is an indication to discontinue IL-2 until SVT resolves. If patient is hemodynamically unstable, this should be treated with Digoxin or cardioversion **NOT** verapamil (which may result in severe hypotension)
- e) **Renal Dysfunction:** Most patients will develop oliguria and some elevation of serum creatinine ($\leq 2.0 \times$ baseline) during induction IL-2 due to decreased renal perfusion, intrinsic renal effects of IL-2 and indomethacin. This is usually quickly reversible after induction IL-2 is completed.

i) The common manifestations of IL-2 induced renal dysfunction are:

Weight gain of 1-10% of baseline body weight.
Metabolic acidosis (total CO₂ 15-20).
Lowering of serum K+, Mg++, Phos+.

ii) During induction IL-2 therapy, these guidelines should be followed:

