- a. Allow the patients to gain \leq 1-1.5%/day of baseline body weight.
- b. Reserve diuretic therapy for patients with symptomatic interstitial edema (i.e., pulmonary edema, or ascites). Overly aggressive diuresis for asymptomatic patients with weight gain and oliguria will often result in hypotension and worsening of renal dysfunction.
- c. If creatinine increases by $<$ 50% over baseline, reduce indomethacin to q 12 hr.
- d. If creatinine increases by \geq 50% over baseline, discontinue indomethacin.

e) **Hematologic Side Effects – Background:**

IL-2 therapy causes the following hematologic effects.

- i) **Lymphocytosis** as high as 20-50,000/mm³ occurs often and is maximal 24 hours after stopping induction IL-2; lymphopenia occurs during Days 1-4 of induction IL-2.
- ii) **Anemia** occurs often, due to decreased production and destruction RBC's. Most patients will require RBC transfusions during induction IL-2.
- iii) **Neutrophilia and Eosinophilia** occurs often, and is due to secondary release of GM-CSF, IL-5 and IL-3.
- iv) **Thrombocytopenia** occurs often. Platelet counts are lowest on Days 4-9 of IL-2 therapy, and most patients will require more frequent platelet transfusions during this period.

g) **Infectious Complications:**

- i) All patients should receive prophylactic antibiotics during induction IL-2.

- ii) Blood cultures should be drawn at least once per day for temperature spikes.
- iii) Any fever that persists more than 24 hours after induction IL-2 is completed should suggest a secondary infection and **NOT** be ascribed to IL-2 until infection has been ruled out.

h) Gastrointestinal Toxicity:

Nausea, vomiting and diarrhea are common during induction IL-2. Most patients have a limited oral intake during this time. These symptoms usually improve quickly once IL-2 is discontinued.

i) Hepatic Toxicity:

- i) Cholestasis with elevated bilirubin and alkaline phosphatase is common, usually peaks on Day 5-7 and quickly resolves.
- ii) Drugs which are hepatically metabolized may need temporary dose reductions during this period of hepatic dysfunction.

j) Neurologic Toxicity:

- i) Neurologic abnormalities such as lethargy, mild confusion, subtle personality change and memory disturbance occur in some patients receiving narcotics, sedatives or antiemetics concomitantly with IL-2. Patients with these symptoms should have psychoactive drugs reduced or discontinued.

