- ii) In any patient who develops \geq Grade 2 neurologic toxicity, IL-2 will be discontinued immediately and permanently.

7.0 COMPLICATIONS OF THERAPY:

Busulfan: Human toxicity from busulfan includes: a) Severe bone marrow hypoplasia which could be fatal without administration of bone marrow or peripheral blood stem cells. b) Nausea and vomiting which can be decreased by the use of sedation and antiemetics. c) Stomatitis and diarrhea which can be treated symptomatically with fluid replacement and atropine or diphenoxylate Hcl. d) Pulmonary fibrosis characterized by delayed onset of cough, shortness of breath and low grade fever. e) Hepatic damage which can occur in combination with melphalan or as a single agent and can result in significant hepatic toxicity which can be fatal. f) Temporary hyperpigmentation of the skin and nail bed changes. g) Grand mal seizures which can be prevented by the prophylactic administration of dilantin.

Total body irradiation: The short term and long term complications of TBI have been reviewed by others. Most patients will experience nausea and vomiting. This problem will be managed symptomatically and usually resolves within 24 hours of ending therapy. Oral mucositis is expected in virtually all patients. Mouth care will be performed with hydrogen peroxide and clotrimazole. Only toothbrushes will be allowed. Pain will be managed with morphine or dilaudid. All patients should expect permanent sterility. It is probable that most patients will be infertile from previous therapy, but male patients will be offered the option of semen storage before therapy. Temporary alopecia will also be expected in all patients. Long term survivors may develop cataracts within a few years following BMT. These can be managed successfully in the same way as cataracts, unrelated to radiation. Solid tumors have been seen following TBI. Radiation fibrosis of the lung and hypothyroidism are also potential but unlikely complications.

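### For a first Grade 2 or higher neurologic toxicity on IL-2, Section 6.65 a) allows a restart at half dose while Section 6.66 j) ii requires a permanent stop

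*Combined protocol and SAP*

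**What the plan says.** Section 6.65 a) sets the dose-modification rule for IL-2. Any Grade 3 or 4 toxicity interrupts treatment, and a parenthesis names further triggers: "or Grade 2 neurologic or cardiac toxicity; Grade 4 neutrophils or bilirubin; or platelets" below a stated count despite transfusion. After interruption the patient waits for return to Grade 1, "at which time IL-2 therapy will be resumed at 50% of the initial dose". IL-2 is ended for good only under a second condition: "If Grade 3 or 4 toxicity, or Grade 2 neurotoxicity or cardiac toxicity, recurs after resumption of the reduced dose of IL-2". Neurologic toxicity is therefore named twice, once as a reason to hold and restart, and once as a reason to stop on recurrence.

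Section 6.65 b) keeps the calendar fixed: "Any doses missed due to toxicity are not administered", and treatment is not extended.

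Section 6.66 j) ii covers any patient who develops neurologic toxicity at or above the grade named: "Grade 2 neurologic toxicity, IL-2 will be discontinued immediately and permanently". It has no recurrence condition and no restart.

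Two cross-references bear on precedence. Section 6.63 d) ii refers other toxicities during maintenance IL-2 to Section 6.66. Section 6.66 b), in the item on capillary leak syndrome, points the other way: "Dose modifications are made for specific organ system toxicity, as per Section 6.65".

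**The concern.** For the same first event, one section puts the patient back on the drug and the other forbids it. A clinician who follows the section titled Dose Modification would re-expose a patient whom Section 6.66 takes off IL-2. By the schedule in 6.61 b) ii, re-exposure after induction is in the outpatient setting by default.

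There is also a smaller statistical consequence. Section 8.1 evaluates IL-2 by feasibility of administration and tolerability. The same event could be recorded as continuation at reduced dose under one rule and as discontinuation under the other, so the tolerability summary would partly reflect which section was read.

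**Working it through.** **Step 1. The two rules side by side.**

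| Event | Section 6.65 a) | Section 6.66 j) ii |
|---|---|---|
| First Grade 2 neurologic | Hold, restart at 50% on return to Grade 1 | Permanent stop |
| First Grade 3 or 4 neurologic | Same, through the general Grade 3 or 4 trigger | Permanent stop |
| Recurrence at reduced dose | Permanent stop | Cannot arise |

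The first two rows contradict each other. The third shows that 6.66 j) ii cannot be read as a mere detail of 6.65 a): if it governs, the neurotoxicity clause in the recurrence sentence can never apply.

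**Step 2. Does any text give precedence?** No sentence does so outright. For events that begin in maintenance, 6.63 d) ii leads to 6.66 and so to the permanent stop. For events that begin in induction there is no such pointer. The reference from 6.66 b) back to 6.65 sits in the capillary leak item, so it does not clearly reach neurologic events. Section 6.65 a) names neurologic toxicity without limiting it to a course.

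**Step 3. How much IL-2 separates the rules?** The plan states no cumulative dose, so there is no figure to reproduce. Inputs from the table in 6.61 b) ii are 9.0 x 10^6 IU/m2 per day on Days 1-4 and 1.6 x 10^6 IU/m2 per day on Days 9-18.

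- Planned total: 4 x 9.0 + 10 x 1.6 = 36 + 16 = 52 (all in 10^6 IU/m2).
- Assumption: the initial dose means the daily dose of the course in progress. Half of the induction dose would be 4.5 per day, above the planned maintenance dose of 1.6, so that reading is implausible for maintenance.
- Under 6.66 j) ii nothing more is given. Under 6.65 a) at most half of the remaining dose is given, and nothing if Grade 1 is not reached before the schedule ends on the morning of Day 19.
- Gap = 0 to 0.5 x (dose still due).

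| Event at end of | Given | Still due | Gap | Gap / 52 |
|---|---|---|---|---|
| Day 2 | 2 x 9.0 = 18 | 18 + 16 = 34 | 0 to 17 | 0 to 32.7% |
| Day 4 | 36 | 16 | 0 to 8 | 0 to 15.4% |
| Day 13 | 36 + 5 x 1.6 = 44 | 5 x 1.6 = 8 | 0 to 4 | 0 to 7.7% |

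For the Day 4 event, 6.66 j) ii delivers 36/52 = 69.2% of plan, and 6.65 a) delivers between that and 44/52 = 84.6%. Days 5-8 are rest, so the upper end needs only return to Grade 1 by the morning of Day 9. For Days 2 and 13 the upper end needs immediate recovery. Day 4 is shown because 6.66 a) describes "dose and time dependent toxicities which peak toward the end of the induction course". The common toxicities listed there are flu-like, so it is a reference day and not an estimate of when neurologic events occur.

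**The case against.** The strongest defence is that the stricter, organ-specific rule in 6.66 governs and that clinicians would follow it. For maintenance-onset events this has force, because 6.63 d) ii leads there. It does not settle induction-onset events, because 6.65 a) is itself specific and names neurologic toxicity in both its sentences.

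A second defence is that re-exposure is mild and supervised. A maintenance restart would be at 0.8 x 10^6 IU/m2 per day, which is 0.8/9.0 = 8.9% of the induction daily dose. Section 6.61 b) ii allows admission where clinically indicated, and 6.63 c) discourages routine ancillary drugs in maintenance. This stands and limits the harm, but it does not say which rule applies. Section 8.4 lists neurotoxicity at day 100 among its severe complications. That is a trial-level check and does not decide an individual patient's dosing.

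Three stronger readings are tempting and are not supported.

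- A reader might infer that events of Grade 2 or higher are expected. Section 6.66 j) i describes "lethargy, mild confusion, subtle personality change and memory disturbance occur in some patients receiving narcotics, sedatives or antiemetics concomitantly with IL-2", and its remedy is to reduce the psychoactive drugs. It gives no grade and no frequency.
- A reader might infer from the second institution in Appendix IIa that sites will diverge. That appendix is a radiation schema and says nothing about IL-2.
- A reader might infer that the stop sentence in 6.65 a) also fails to match its hold triggers for neutrophils, bilirubin and platelets. The parenthesis opens with an additive word, so Grade 3 neutrophils and bilirubin already fall under the general trigger. The mismatch arises mainly if that word is read as an exception. Even then, the reference to recurrence points back to the toxicity that caused the hold.

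**Conclusion.** The contradiction is real and stands in current text: a first neurologic toxicity of Grade 2 or higher leads to a half-dose restart under 6.65 a) and to a permanent stop under 6.66 j) ii. It is clearest for induction-onset events and partly resolved by routing for maintenance-onset events.

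The difference is at most half of the IL-2 still due, for example 0 to 15% of the planned dose for an event at the end of Day 4. That bound rests on reading the 50% as half of the daily dose of the course in progress. The contradiction itself rests on no calculation.

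Severity is minor. The number of patients affected cannot be estimated from the documents, and no sample size, analysis or IL-2 decision rule depends on it. It still merits correction, because it concerns when a drug is stopped for safety and it feeds the tolerability evaluation in 8.1.

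**What to change.** In Section 6.65 a), delete neurologic toxicity from the hold-and-restart list and neurotoxicity from the recurrence sentence, and add: *Neurologic toxicity of Grade 2 or higher is a permanent stop; see 6.66 j) ii, which overrides this section.* The added sentence is needed as well as the deletions, because Grade 3 and 4 neurologic events would otherwise still restart through the general trigger. If the study team intends a restart, amend 6.66 j) ii instead. Leave the Grade 1 restart level for other toxicities as written.

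The cost is amendment wording, with no new data or visits. Under the dose assumption above, an affected patient forgoes at most half of the IL-2 still due. This is modest late in the schedule but up to 17 of 52 x 10^6 IU/m2 (33%) for an event at the end of Day 2, so the team should make the choice knowingly.

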6.66 Toxicities of IL-2 Therapy

- a) High-dose IL-2 administered by CIV results in dose and time dependent toxicities which peak toward the end of the induction course. The most common clinical toxicities seen during induction

IL-2 are of a flu-like syndrome with fever, chills, weight gain, nausea, diarrhea, and rash.

- b) Capillary Leak Syndrome (CLS): The CLS is characterized by peripheral or pulmonary interstitial edema and/or ascites, and "sepsis-like" physiology, i.e., decreased systemic vascular resistance and increased cardiac output. Dose modifications are made for specific organ system toxicity, as per Section 6.65.
- c) Hypotension: Mild hypotension with systolic blood pressure (SBP) 10-20% below baseline is common in patients receiving induction IL-2.
 - i) Asymptomatic patients with SBP > 90 mm Hg should be monitored closely.
 - ii) Any symptomatic patient (regardless of the SBP) and all patients with SBP ≤ 85 mm Hg should be treated immediately with a fluid bolus of NS, 5-7 ml/kg (STAT x 1-2) which may be supplemented with red cell transfusions or colloid infusion. Hypotension which does not respond to fluid therapy should be treated with low-dose dopamine or a phenylephrine infusion, and IL-2 therapy should be interrupted until hypotension resolves.
 - iii) Grade 3 hypotension which does not respond to crystalloid/colloid therapy requires:

IV pressors, preferably phenylephrine (rather than dopamine).

Discontinuing IL-2 infusion

d) Arrhythmias:

- i) Sinus Tachycardia: is common, especially during fever, and is not an indication for intervention.
- ii) Supraventricular Tachycardia: Occurs in $< 10\%$ of adult patients and is an indication to discontinue IL-2 until SVT resolves. If patient is hemodynamically unstable, this should be treated with Digoxin or cardioversion **NOT** verapamil (which may result in severe hypotension)
- e) **Renal Dysfunction:** Most patients will develop oliguria and some elevation of serum creatinine ($\leq 2.0 \times$ baseline) during induction IL-2 due to decreased renal perfusion, intrinsic renal effects of IL-2 and indomethacin. This is usually quickly reversible after induction IL-2 is completed.

i) The common manifestations of IL-2 induced renal dysfunction are:

Weight gain of 1-10% of baseline body weight.
Metabolic acidosis (total CO₂ 15-20).
Lowering of serum K+, Mg++, Phos+.

ii) During induction IL-2 therapy, these guidelines should be followed:

- a. Allow the patients to gain \leq 1-1.5%/day of baseline body weight.
- b. Reserve diuretic therapy for patients with symptomatic interstitial edema (i.e., pulmonary edema, or ascites). Overly aggressive diuresis for asymptomatic patients with weight gain and oliguria will often result in hypotension and worsening of renal dysfunction.
- c. If creatinine increases by $<$ 50% over baseline, reduce indomethacin to q 12 hr.
- d. If creatinine increases by \geq 50% over baseline, discontinue indomethacin.

e) **Hematologic Side Effects – Background:**

IL-2 therapy causes the following hematologic effects.

- i) **Lymphocytosis** as high as 20-50,000/mm³ occurs often and is maximal 24 hours after stopping induction IL-2; lymphopenia occurs during Days 1-4 of induction IL-2.
- ii) **Anemia** occurs often, due to decreased production and destruction RBC's. Most patients will require RBC transfusions during induction IL-2.
- iii) **Neutrophilia and Eosinophilia** occurs often, and is due to secondary release of GM-CSF, IL-5 and IL-3.
- iv) **Thrombocytopenia** occurs often. Platelet counts are lowest on Days 4-9 of IL-2 therapy, and most patients will require more frequent platelet transfusions during this period.

g) **Infectious Complications:**

- i) All patients should receive prophylactic antibiotics during induction IL-2.

- ii) Blood cultures should be drawn at least once per day for temperature spikes.
- iii) Any fever that persists more than 24 hours after induction IL-2 is completed should suggest a secondary infection and **NOT** be ascribed to IL-2 until infection has been ruled out.

h) Gastrointestinal Toxicity:

Nausea, vomiting and diarrhea are common during induction IL-2. Most patients have a limited oral intake during this time. These symptoms usually improve quickly once IL-2 is discontinued.

i) Hepatic Toxicity:

- i) Cholestasis with elevated bilirubin and alkaline phosphatase is common, usually peaks on Day 5-7 and quickly resolves.
- ii) Drugs which are hepatically metabolized may need temporary dose reductions during this period of hepatic dysfunction.

j) Neurologic Toxicity:

- i) Neurologic abnormalities such as lethargy, mild confusion, subtle personality change and memory disturbance occur in some patients receiving narcotics, sedatives or antiemetics concomitantly with IL-2. Patients with these symptoms should have psychoactive drugs reduced or discontinued.
- ii) In any patient who develops \geq Grade 2 neurologic toxicity, IL-2 will be discontinued immediately and permanently.

7.0 COMPLICATIONS OF THERAPY:

Busulfan: Human toxicity from busulfan includes: a) Severe bone marrow hypoplasia which could be fatal without administration of bone marrow or peripheral blood stem cells. b) Nausea and vomiting which can be decreased by the use of sedation and antiemetics. c) Stomatitis and diarrhea which can be treated symptomatically with fluid replacement and atropine or diphenoxylate Hcl. d) Pulmonary fibrosis characterized by delayed onset of cough, shortness of breath and low grade fever. e) Hepatic damage which can occur in combination with melphalan or as a single agent and can result in significant hepatic toxicity which can be fatal. f) Temporary hyperpigmentation of the skin and nail bed changes. g) Grand mal seizures which can be prevented by the prophylactic administration of dilantin.

Total body irradiation: The short term and long term complications of TBI have been reviewed by others. Most patients will experience nausea and vomiting. This problem will be managed symptomatically and usually resolves within 24 hours of ending therapy. Oral mucositis is expected in virtually all patients. Mouth care will be performed with hydrogen peroxide and clotrimazole. Only toothbrushes will be allowed. Pain will be managed with morphine or dilaudid. All patients should expect permanent sterility. It is probable that most patients will be infertile from previous therapy, but male patients will be offered the option of semen storage before therapy. Temporary alopecia will also be expected in all patients. Long term survivors may develop cataracts within a few years following BMT. These can be managed successfully in the same way as cataracts, unrelated to radiation. Solid tumors have been seen following TBI. Radiation fibrosis of the lung and hypothyroidism are also potential but unlikely complications.

Autologous PSC Reinfusion: Side effects from the bone marrow and peripheral stem cell infusion should be minimal. Volume overload may be seen, but can be managed with diuretics. Fevers and chills may occasionally be encountered. At the University of Nebraska at least two patients developed acute abdominal pain of unknown cause during their marrow infusions. The pain was managed with narcotic analgesics and resolved spontaneously. The lysis of frozen erythrocytes may be associated with hemoglobinuria. Patients will have positive tests for blood in the urine, but no erythrocytes will be found in the sediment. At the University of Nebraska three patients developed acute renal failure after autologous bone marrow infusion. This problem was presumed to be due to hemoglobinuria and was no longer seen after red blood cells were removed from the marrow prior to cryopreservation. This is not expected to be a problem since we will also be removing the red cells with Ficoll-Hypaque. DMSO will be infused along with the bone marrow. It is excreted through the lungs and its characteristic odor may be noticeable for a few days after marrow infusion.

8.0 STATISTICAL CONSIDERATIONS:

8.1 Primary and Secondary Endpoints: The primary endpoints of this Phase II study are to evaluate the toxicity and efficacy of FTBI/VP-16 and targeted Busulfan dosage for AUC 700-900 as a preparative regimen for autologous BMT with primed peripheral stem cells following consolidation therapy with high dose Ara-c and idarubicin or high dose Ara-c alone in patients with AML in first complete remission (CR). Complete remission will be defined as neutrophils >1500/ml and platelets >100,000. Efficacy will be estimated as 2 and 5 year disease-free survival (DFS). The role of IL-2 following autologous BMT will also be evaluated based on feasibility of administration and ability to tolerate IL-2. The effect of cytogenetics, WBC at presentation, AUC of Busulfan and number of courses of induction therapy to achieve remission will be evaluated as possible prognostic factors for relapse, DFS, and overall survival.

8.2 Sample Size Estimation and Length of Accrual: A total of 50 patients with AML in first CR and less than \leq 60 years old will be accrued to this trial, so that in estimating the engraftment and relapse rates the maximum standard error will be 0.07. We expect to accrue approximately 10-12 patients per year so that this trial will require 4-5 years for completion.

8.3 Statistical Analyses: The rate of engraftment and median time to engraftment will be estimated, defined as time to ANC>500 and platelets > 20,000.

The Kaplan-Meier method will be used to estimate time to relapse, DFS, and overall survival, and 95% confidence intervals will be calculated using Greenwold's variance. All patients receiving HD Ara-c and Idarubicin consolidation will be included in the analysis for intent-to-treat with autologous BMT. For overall survival, failure time will be calculated from the day of first consolidation treatment to the day of death due to any cause for those patients who fail. For DFS, the failure time will be calculated from the day of first treatment to the day of disease relapse or death due to any cause. For patients who remain alive and well at the time of analysis, the survival time will be censored as of the date of last contact.

A further analysis of time to relapse, DFS and overall survival will be carried out for the subset of patients who go on to autologous BMT, with survival estimates calculated from the day of transplant. The Cox proportional hazard regression model will be used to analyze possible prognostic factors for relapse, DFS and overall survival.

8.4 Early Stopping Rules: If at any time the severe treatment related complication rate (e.g. severe VOD, interstitial pneumonia, neurotoxicity at day 100 post ABMT), exceeds 10%, with a high probability (i.e. 95%) then further accrual to the trial will be terminated. Similarly if with a high probability (95%) the regimen related mortality at day 100 post ABMT exceeds 10% the trial will be terminated. This would occur if the following numbers of events have been observed, monitoring after every set of 10 patients it accrued:

Number of Patients Accrued	Number of Adverse Events Leading to Early Termination
10	4
20	5
30	7
40	8

Rev. 5/7/01

We will stop accrual of good risk cytogenetic patients on the study if the good risk cytogenetic patients demonstrate excess relapse. Based on previous COH experience, good risk cytogenetic patients have a relapse rate of 13%. The study will close if the lower bound of an estimate of the true rate of relapse exceeds 15% for the subgroup. Evidence of relapse will be taken as the lower limit associated with an exact 95% one-sided confidence interval for proportions. Table 1 below shows the critical points for early stopping of accrual.

Table 1: Critical points for early stopping for relapse

Critical points for early stopping	95% one-sided CI
Cumulative enrollment of good risk cytogenetic patients	Conclude omitting idarubicin poses a safety threat in >15% of pts if N experiencing relapse is at least:
5	3
10	4
15	6
20	7

25	8
30	9
35	10

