6.62 Supportive Care During IL-2 Therapy

a) **Intravenous Fluid Administration**

During induction IL-2 therapy, patients retain sodium and free water and generally exhibit and tolerate weight gain of 5-10% of initial body weight. Aggressive sodium and free water restriction may result in hypotension whereas aggressive sodium and fluid administration may result in pulmonary edema and/or ascites. IV fluid therapy during induction IL-2 should be begun as follows, and adjusted according to the patient's subsequent clinical course:

- i) The patient should receive IV hydration with normal saline (NS) at 500 cc/m²/24 hr.
- ii) The patient's total daily IV intake should be limited to \leq 1.5 L/m²/24 hr.

b) **Prophylactic Antibiotics**

IL-2 causes a reversible defect in neutrophil function. Fevers are almost universal during induction IL-2 therapy and usually do not signify infection. However, gram positive, and rarely gram negative, infections occur in 10-25% of patients. These infections can be serious and, therefore, prophylactic antibiotics should be administered as follows (choice of antibiotics may be altered due to a patient history of sensitivity to these medications). Patients are to receive Levaquin 500mg p.o. q.d. while receiving IL-2.

Revised 3/11/02

c) **Ancillary Medications**

To decrease IL-2 toxicity, the following medications are recommended during IL-2 therapy. Alterations may be made based on individual patient factors. **NOTE:** One dose of acetaminophen, diphenhydramine and naprosyn should be administered prior to each dose of IL-2 during the first week. Then for the subsequent weeks acetaminophen should be administered prior to each dose of IL-2. Other medications that could be used for symptom control or prevention are listed below:

- i) **Acetaminophen:** 650 mg PO 30 minutes before first dose of IL-2 is administered and q 4-6 hr as needed for fever.

- ii) **Diphenhydramine:** 50 mg PO 30 minutes before first dose of IL-2 is administered then 25-50 mg PO or IV q 4-6 hours prn for nausea, pruritis.
- iii) **Pepcid:** 20 mg PO or I.V. BID.
- iv) **Meperidine:** 25-50 mg IV q 2 hr or 50 to 150mg po prn for chills
- v) **Prochlorperazine:** 10mg IV or PO q 6 hr prn for nausea.
- vi) **Naproxsyn:** 375 mg PO 30 minutes prior to IL-2, then q 12° for fever/myalgia
- vii) **Contraindicated Medications:** See section 6.64

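### Acetaminophen pre-dosing in 6.62c carries into maintenance IL-2, where 6.63c says to avoid it; as a lesser point, the 6.66e creatinine steps omit naproxen

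*Combined protocol and SAP*

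**What the plan says.** **Acetaminophen.** Section 6.62 is headed as supportive care during IL-2 therapy in general, and the lead-in to its part c recommends the ancillary list for IL-2 therapy without naming a phase. The NOTE then sets pre-dosing: "One dose of acetaminophen, diphenhydramine and naprosyn should be administered prior to each dose of IL-2 during the first week". Its next sentence keeps acetaminophen alone going, before each IL-2 dose, in the weeks that follow. Item i adds acetaminophen every 4-6 hours as needed for fever. Section 6.63, the maintenance section, gives levofloxacin prophylaxis. Its part c then says that no further ancillary drug should be routine and that Tylenol and Indocin should be avoided because they can hide infection. Part d treats fever in maintenance as a strong sign of infection and rules out antipyretics alone until infection has been assessed.

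**Naproxen.** Item vi of 6.62c gives the dose: "375 mg PO 30 minutes prior to IL-2, then q 12" hours, for fever or myalgia. Indomethacin is not on that list. Section 6.66e, on renal dysfunction in induction, says "Most patients will develop oliguria and some elevation of serum creatinine", up to 2.0 times baseline, and gives among the causes "intrinsic renal effects of IL-2 and indomethacin". For a rise below 50%, step c says to "reduce indomethacin to q 12 hr". Step d, for a rise of at least that size, reads "50% over baseline, discontinue indomethacin". Neither step mentions naproxen.

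**The concern.** Maintenance IL-2 is normally given to outpatients. Section 6.62b says IL-2 impairs neutrophil function, and 6.6 A lets patients start once the neutrophil count has exceeded 500/mm³ for three days. Fever is therefore the warning sign that 6.63d relies on. A clinician working from the 6.62c NOTE would be pre-treating that sign with the drug that 6.63c says to avoid.

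In induction, a clinician who gives naproxen as 6.62c directs, and then sees creatinine rise, finds a rule written for a different drug. The step d trigger is a 50% rise, or 1.5 times baseline. That lies inside the range (up to 2.0 times baseline) that 6.66e expects, so the situation is foreseeable.

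**Working it through.** There is no plan figure to reproduce. The check sets the instructions against the treatment calendar.

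**1. Which IL-2 falls after the first week?** From 6.61b:

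| Phase | Days | Week |
|---|---|---|
| Induction | 1-4, ending the morning of Day 5 | 1 |
| Rest | 5-8 | 1 into 2 |
| Maintenance | 9-18, ending the morning of Day 19 | 2-3 |

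Week 1 is Days 1-7. Induction ends inside it, and no IL-2 is given again until Day 9. Delays for toxicity do not change this: under 6.65b missed doses are not made up and treatment resumes by the original calendar, so induction cannot spill into a later week. The NOTE's sentence about later weeks can therefore refer only to maintenance.

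**2. Do the two instructions meet?** Same drug (acetaminophen, Tylenol), same period (Days 9-18), opposite direction. In 6.62c it should be given before each dose; in 6.63c it should be avoided and nothing of the kind should be routine. Neither section cites the other as overriding.

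**3. How many pre-doses are affected?** The NOTE counts IL-2 doses, but maintenance is a continuous infusion, so the count depends on the reading:

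- One infusion counted as one dose: 1 pre-dose.
- The mid-course solution change (6.61c iii) starts a second dose: 2.
- Each day's cassette (4.43.3) is a dose: 18 − 9 + 1 = 10.

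The documents do not choose among these.

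**4. Is there a creatinine rule for naproxen anywhere in the IL-2 sections?**

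- 6.62c: gives naproxen, with no creatinine trigger.
- 6.63: no creatinine rule.
- 6.64: the contraindicated list does not include NSAIDs.
- 6.65: modifies IL-2 only, not supportive drugs.
- 6.66e steps c-d: indomethacin only.

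So there is none. For a patient on indomethacin, steps c and d work as written. For a patient on naproxen, step c asks for nothing that is missing, since naproxen is already given every 12 hours. The gap is confined to step d.

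**The case against.** **Acetaminophen.** The best reply is that 6.63 is the dedicated maintenance section and a sensible reader lets it prevail; 6.62a, on fluids, is written for induction, so the whole of 6.62 may have been meant that way. Much of this stands: 6.63c probably would be followed. But neither the heading of 6.62 nor the lead-in to its part c limits the drug list to induction, the sentence on later weeks has no meaning within a four-day induction, and no text ranks the sections. A reader might infer that fever would be masked throughout the maintenance infusion. The documents do not support that, because the NOTE attaches to doses and the number of doses is unclear.

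**Naproxen.** It is fair to say that silence about a second drug is not a conflict. The list is a recommendation, and 6.62c adds that "Alterations may be made based on individual patient factors". Entry to IL-2 limits creatinine (6.6 E), induction is inpatient, 6.65 interrupts IL-2 for Grade 3 or 4 toxicity, and 6.66e says of the renal change that "This is usually quickly reversible after induction IL-2 is completed". All of this stands and keeps the point minor. None of it supplies an instruction to stop naproxen.

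A reader might also infer that the plan contradicts itself on NSAIDs, or that continued naproxen would distort the assessment of IL-2 tolerability in 8.1. The first fails because no two instructions oppose each other. The second fails because the documents give no rate of creatinine rises of 50% or more and do not say that naproxen causes them.

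**Conclusion.** The acetaminophen instructions in 6.62c and 6.63c contradict each other for maintenance (Days 9-18). This is the main point. It rests on the 6.61b calendar and on reading Tylenol as acetaminophen. It should be corrected because the opposing instructions concern recognition of infection in outpatients, although 6.63c is the more specific and would probably be followed.

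The naproxen point is secondary and minor: the creatinine steps name an NSAID that 6.62c does not list and omit the one it has staff give in the induction week. Extending step d assumes that naproxen should be handled like indomethacin when creatinine rises. That is a reasonable clinical judgement, but the documents do not state it.

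Harm is not quantified for either point. Neither affects the design, sample size, stopping boundaries or survival analyses.

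**What to change.** 1. In 6.62c, limit the ancillary list to induction. This must cover the lead-in, the NOTE, and items i (acetaminophen as needed for fever) and vi (naproxen for fever or myalgia). If only the NOTE were changed, those items would still apply to all IL-2 therapy.
2. Delete the NOTE's sentence on later weeks and add: *for maintenance see 6.63c-d*.
3. In 6.66e ii, reword the action in step d as: *discontinue indomethacin, naproxen or any other NSAID in use*. Step c can stay as it is.

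The cost is a short wording amendment to two sections. No visit, test, sample size or analysis changes.
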